6. TRIAL OBJECTIVES AND PURPOSE

To evaluate the utilization and safety of the Mk II inserter and to evaluate the safety of the FAI insert in eyes with non-infectious uveitis affecting the posterior segment of the eye.

6.1. **Primary Objective**

To assess the utilization and the safety of the Mk II inserter, and the safety of the FAI insert, from the day of treatment through 7 days following treatment.

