11.2. Adverse Event Assessment

11.2.1. Relationship to Study Treatment

The study treatment relationship to each AE should be determined by the Investigator using these explanations:

Unrelated: Evidence indicates no plausible direct relationship to the study medication, device or procedure, or there is a reasonable causal relationship between non-investigational product, concurrent disease, or circumstance and the AE.

Possibly Related: There is reasonable causal relationship between the investigational product, device or procedure and the AE suggests that the association of the event with the study medication, device, or procedure is unknown; however, the adverse event is not reasonably supported by other conditions.

Probably Related: Suggests that a reasonable temporal sequence of the event with medication administration, device usage or the index procedure exists and, based upon the

Investigator's clinical experience, the association of the event with study medication, device or procedure is likely.

The Investigator will make the determination of relationship to the investigational product for each AE (Unrelated, Possibly Related or Probably Related). The Investigator should decide whether, in his or her medical judgment, there is a reasonable possibility that the event may have been caused by the investigational product, device or procedure. If no valid reason exists for suggesting a relationship, then the AE should be classified as "unrelated".

If there is any valid reason, even if undetermined, for suspecting a possible cause-and-effect relationship between the investigational product and the occurrence of the AE, then the AE should be considered as related.

If the relationship between the AE/SAE and the investigational product is determined to be "possible" or "probable" the event will be considered to be related to the investigational product for the purposes of expedited regulatory reporting.

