11.3. Recording of Adverse Events

Medical conditions or diseases present before a subject starts study treatment are only considered AEs if they worsen after the start of the study treatment.

Adverse events can be spontaneously reported or elicited at each study visit through open-ended questioning, examination or evaluation of a subject. In order to prevent reporting bias, subjects should not be questioned regarding the specific occurrence of one or more AEs.

The Investigator will record all AEs of enrolled subjects in the appropriate eCRF. If known, the diagnosis of the underlying illness or disorder should be recorded, rather than its individual symptoms.

The following information should be captured for all AEs: onset and end date, severity, seriousness, relationship to investigational product, action taken, treatment required and outcome. If treatment for the AE was administered, it should be recorded on the appropriate eCRF page.

Completion of supplemental eCRF pages may be requested for AEs and/or laboratory abnormalities that are reported / identified during the course of the study.

The Investigator will take or organize all appropriate and necessary therapeutic measures required for resolution of the adverse event. Any medication necessary for the treatment of an adverse event must be recorded on the concomitant medication eCRF. If more than one distinct AE occurs, each event should be recorded separately.

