11.4.1. Reporting of Serious Adverse Event

All SAEs that occur during the course of the study, including death, *must be reported within 24 hours following the site's knowledge of the SAE* and recorded on the Serious Adverse Event eCRF (or use a back-up paper form if the eCRF system is not functioning). SAEs will also be reported to regulatory authorities and IRBs/ECs based on the applicable regulatory requirements.

Minimal information to be provided includes:

- Identification of the study
- Identification of the initial reporter
- Patient identification number
- Event term
- Date of onset of the event
- Severity criteria of the event
- Reporting criteria
- Narrative description of the event
- Outcome if known
- Causal relationship to the investigational medication, device and procedure
- Additional and follow-up information as requested by the medical monitor

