14.3.6. Analyses of Safety

Safety analyses will be performed on the safety population at Day 7 and Month 12. Eyes randomized but not receiving treatment will have all safety data listed only but will not be included in safety tabulations. Descriptive statistics will be provided for all adverse events. Frequency counts and percentage of eyes within each category will be provided for categorical data. Treatment Emergent Adverse Events (TEAEs; those that occurred on the day or after treatment) will be coded to a corresponding preferred term from the MedDRA coding dictionary.

Ocular safety will be assessed by evaluating ocular TEAEs, visual acuity, IOP, concomitant medications, and slit lamp / dilated indirect ophthalmoscopy exams. Systemic safety will be assessed by evaluating all TEAEs, vital signs, concomitant medications and clinical laboratory tests by treatment group.

Adverse events will be summarized by presenting the number and percentage of eyes having at least one occurrence of any TEAE during the study, having at least one occurrence of a TEAE within each system organ class, and having at least one occurrence of each individual TEAE (preferred term) in each treatment group. Occurrence of TEAEs using MedDRA preferred term, System Organ Class (SOC), by severity and relationship will be provided by treatment group. If a patient experiences multiple events that map to a single preferred term, the greatest severity and strongest Investigator assessment of relation to the investigational product will be assigned to the SOC and preferred term for the appropriate summaries.

Treatment-emergent serious adverse events (SAEs) and TEAEs related to FAI insert treatment will be provided by preferred term, SOC and severity for each treatment group. Again, if a patient experiences multiple events that map to a single preferred term, the greatest severity and strongest Investigator assessment of relation to the investigational product will be assigned to the SOC and preferred term for the appropriate summaries. Adverse events leading to study discontinuation and any deaths will be listed.

Vital signs will be presented using descriptive statistics by visit in each treatment group. Concomitant medication will be summarized by presenting the number and percentage of subjects receiving each medication by term and treatment after coding with WHO-Drug Dictionary terms. Laboratory assessments will be presented by descriptive statistics.

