9.1.2. Relationship of Adverse Events to Study Treatment

A summary of TEAEs by relationship to study treatment will be presented in a table by incidence of occurrence by treatment group. The investigator will provide an assessment of the relationship of the event to the study treatment. The possible relationships are "Unrelated", "Possibly Related", and "Probably Related". TEAEs that are missing a relationship will be presented in the summary table as "Probably Related" but will be presented in the data listing with a missing relationship.

The TEAE data will be categorized and presented by SOC, PT, and relationship in a manner similar to that described in Section 9.1.1.

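### The plan specifies one investigator relationship rating per adverse event for drug, device and injection together, so related events cannot be attributed by source

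*Protocol*

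**What the plan says.** The primary objective (Protocol 6.1) names two safety questions: "To assess the utilization and the safety of the Mk II inserter, and the safety of the FAI insert". Protocol 13.3 likewise lists procedure-related adverse events as an endpoint separate from all other adverse events.

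Protocol 11.2.1 defines Unrelated, Possibly Related and Probably Related against drug, device and procedure jointly, and tells the investigator to judge whether there is a reasonable possibility that "the event may have been caused by the investigational product, device or procedure". Other sentences in the same section word the determination against the investigational product alone.

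For every adverse event, Protocol 11.3 calls for "onset and end date, severity, seriousness, relationship to investigational product, action taken, treatment required and outcome". That is one relationship item. For serious events, the minimum report in Protocol 11.4.1 includes "Causal relationship to the investigational medication, device and procedure".

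On analysis, SAP 9.1.2 states: "The investigator will provide an assessment of the relationship of the event to the study treatment". SAP 9.1.3 counts Possibly and Probably Related as related. Protocol 14.3.6 says that "TEAEs related to FAI insert treatment will be provided by preferred term, SOC and severity for each treatment group". SAP 9.1.9 adds a clinical review of events with onset within 7 days of the insertion, to judge their relationship to the injection procedure.

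**The concern.** The trial asks about the inserter and the insert separately, but the planned rating has one slot for both. Event type does not always settle the source: Protocol 13.3 lists IOP change and clinically significant ocular changes under procedure-related events and again under all other events. For those, someone has to judge what caused the event, and the investigator at the eye is the obvious person to ask.

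What is at stake is the meaning of the related-event tables. A reader of a table described as related to FAI insert treatment will take it as a statement about the drug product. If it also holds redness from the needle, it overstates what investigators attributed to the insert and does not show what they attributed to the inserter.

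**Working it through.** The plan states no figure on this point, so the check sets the passages side by side.

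| Place | What the relationship refers to | Items specified |
|---|---|---|
| Protocol 11.2.1, category definitions and guiding question | drug, device or procedure | one |
| Protocol 11.2.1, determination and later sentences | investigational product only | one |
| Protocol 11.3, all adverse events | investigational product | one |
| Protocol 11.4.1, serious events | drug, device and procedure all named | one bullet; number of answers unclear |
| Protocol 14.3.6, related table | FAI insert treatment | one |
| SAP 9.1.2 and 9.1.3 | study treatment | one |
| SAP 9.1.9 | injection procedure | separate clinical review, onset within 7 days |

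**Tracing hypothetical events through the plan**

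1. *Eye redness on Day 1, attributed to the needle only.* Unrelated requires that no plausible link to drug, device or procedure exists, so under the definitions the event is Possibly or Probably Related. It enters the related tables, including the one in Protocol 14.3.6. SAP 9.1.9 would also review it and could class it as procedure-related.
2. *The same event, rated by an investigator who follows the sentences about the investigational product alone.* It could be rated Unrelated and leave the related tables. The insert table is then cleaner, but no investigator attribution to the device or injection exists anywhere for a non-serious event.
3. *Raised IOP at Day 28, attributed to the steroid.* It is rated related and enters the same table as event 1. Nothing in the rating tells the two apart.
4. *A procedure-related event with onset on study day 9.* SAP section 4 sets study day = date − treatment date + 1, so 7 days after insertion is study day 8. The Day 7 analysis runs to study day 10. The event falls in that analysis but outside the SAP 9.1.9 window.

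Neither reading of Protocol 11.2.1 gives causality by source. Having both in one section means that sites may differ.

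**Can the effect be sized?** Only by assumption. Let procedure-related rates be 10% and 30% in the two arms, with an independent drug-related rate d in both. The pooled related rate is 1 − (1 − p)(1 − d), so the contrast is 20 × (1 − d) points:

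- d = 5%: 14.5% and 33.5%, contrast 19
- d = 10%: 19% and 37%, contrast 18
- d = 30%: 37% and 51%, contrast 14
- d = 50%: 55% and 65%, contrast 10

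None of these rates is in the documents. The answer depends almost wholly on d, which could be small in a 7-day window for a product designed to release over 36 months. For scale, with 10% of 20 Mk II eyes and 30% of 10 Mk I eyes, the standard error of the difference is √(0.10 × 0.90/20 + 0.30 × 0.70/10) = √0.0255, about 16 points. The loss is at most 10 points anywhere in the range shown.

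**The case against.** A reader might infer that the trial cannot answer its inserter-safety question. The documents do not support that. Eyes are randomized to Mk II or Mk I and all receive the same FAI insert, and Protocol section 2 and SAP 3.2 define inserter safety through ocular adverse events over Day 1 to Day 7. Comparing all such events between arms needs no relationship rating.

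Nor is the plan silent on procedure attribution. SAP 9.1.9 reviews early events and names the obvious candidates, such as eye pain, erythema and IOP change in either direction. Insert-type effects are tabulated without causality too: cataract and raised IOP by coded term (SAP 9.1.8), IOP-lowering medication and surgery (SAP 7.1.3 and 7.2.1), cataract surgery (SAP 7.2.2) and IOP thresholds (SAP 9.2.2). Preferred term and onset date will often point to the source.

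Two limits on the evidence also stand. The adverse event eCRF page is not in the documents, and Protocol 11.3 allows supplemental pages. Protocol 11.4.1 names three sources in one bullet but does not clearly require three answers, and SAP 9.1.4 tabulates none of them. So it cannot be said that the form has only one field, or that serious events are already rated by source.

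All of this narrows the point without removing it. SAP 9.1.9 is not an investigator rating, covers only early onset, does not separate device from injection, and does not ask about the insert. Separate fields, if they exist on the eCRF, are neither described in the protocol nor used in the SAP. SAP 9.1.3 avoids the labelling problem by saying study treatment, but Protocol 14.3.6 does not.

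**Conclusion.** The point holds as a cheap improvement. As specified, a related adverse event cannot be attributed by its rating to the FAI insert, the inserter or the injection. The table of events related to FAI insert treatment would, under the category definitions, include events related only to the device or the procedure. The section that defines the rating is also inconsistent about what is being rated.

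This affects the reading of every related event in the tables for about 30 eyes. It does not affect the primary utilization endpoint, the success criterion or the randomized comparison of ocular events. The safety analyses are descriptive, and no planned test uses a contrast in related-event rates. No size of attenuation can be derived from the documents, so none is claimed.

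A reader might also conclude that investigator ratings should replace the SAP 9.1.9 review. That does not follow. Only subjects are masked, so the investigator who does the insertion knows which inserter was used, and nothing in the documents shows that this rating would be less biased than a separate review. The verdict assumes that the protocol and SAP describe the data actually collected.

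**What to change.** 1. For every adverse event, record separate relationships to the FAI insert and to the inserter or injection procedure, or to all three sources.
2. Align Protocol 11.2.1, 11.3, 11.4.1 and 14.3.6 so that each names the same sources and 11.4.1 states how many answers are expected. A rating of related to any source can be derived from the separate items, so overall related-event summaries can be kept.
3. In SAP 9.1.2 and 9.1.3, tabulate related events by source. Restate the missing-rating rule for each source, since SAP 9.1.2 shows a missing relationship as Probably Related.
4. Report the investigator's procedure relationship alongside the SAP 9.1.9 clinical review, not in place of it.

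The cost is one or two extra eCRF fields per event, matching edits to the protocol and SAP, and slightly more site work, which is minor at about 30 eyes.

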11.2.2. Severity

AE severity is defined as a qualitative assessment of the degree of intensity of an AE as determined by the Investigator or reported to him/her by the subject. The assessment of severity is made irrespective of test article relationship or seriousness of the event and should be evaluated according of the following scale:

Mild: Awareness of event but easily tolerated. Usually transient, requiring no special treatment, and does not interfere with the subject's daily activities.

Moderate: Discomfort enough to cause some interference with usual activity. Traditionally introduces a low level of inconvenience or concern to the subject and may interfere with daily activities, but are usually relieved by simple therapeutic measures.

Severe: Causes an interruption of the subject's usual daily activity and traditionally requires systemic drug therapy or other treatment.

11.3. Recording of Adverse Events

Medical conditions or diseases present before a subject starts study treatment are only considered AEs if they worsen after the start of the study treatment.

Adverse events can be spontaneously reported or elicited at each study visit through open-ended questioning, examination or evaluation of a subject. In order to prevent reporting bias, subjects should not be questioned regarding the specific occurrence of one or more AEs.

The Investigator will record all AEs of enrolled subjects in the appropriate eCRF. If known, the diagnosis of the underlying illness or disorder should be recorded, rather than its individual symptoms.

The following information should be captured for all AEs: onset and end date, severity, seriousness, relationship to investigational product, action taken, treatment required and outcome. If treatment for the AE was administered, it should be recorded on the appropriate eCRF page.

Completion of supplemental eCRF pages may be requested for AEs and/or laboratory abnormalities that are reported / identified during the course of the study.

The Investigator will take or organize all appropriate and necessary therapeutic measures required for resolution of the adverse event. Any medication necessary for the treatment of an adverse event must be recorded on the concomitant medication eCRF. If more than one distinct AE occurs, each event should be recorded separately.

11.4. Adverse Event Reporting

All subjects enrolled in the study will be evaluated for adverse events. For the individual subjects, adverse events will be collected from Day 1 until study completion.

All AEs will be evaluated from their onset until resolution, stabilization, last day of participation in the study of the patient or the last day of the study, whichever is first.

Adverse events that continue after the subject's discontinuation or completion of the study will be followed until their medical outcomes are determined or until no further change in the condition is expected. The event and outcome will be reported in writing by the Investigator to the sponsor. The Investigator shall supply the sponsor and IRB/EC with any additional requested information, notably for reported deaths of subjects.

11.4.1. Reporting of Serious Adverse Event

All SAEs that occur during the course of the study, including death, *must be reported within 24 hours following the site's knowledge of the SAE* and recorded on the Serious Adverse Event eCRF (or use a back-up paper form if the eCRF system is not functioning). SAEs will also be reported to regulatory authorities and IRBs/ECs based on the applicable regulatory requirements.

Minimal information to be provided includes:

- Identification of the study
- Identification of the initial reporter
- Patient identification number
- Event term
- Date of onset of the event
- Severity criteria of the event
- Reporting criteria
- Narrative description of the event
- Outcome if known
- Causal relationship to the investigational medication, device and procedure
- Additional and follow-up information as requested by the medical monitor

11.4.2. Reporting of Pregnancy

To ensure patient safety, each pregnancy in a female subject must be reported by the Investigator, within 24 hours of learning of its occurrence. The pregnancy will also be reported to regulatory authorities and Ethics Committees based on the applicable regulatory requirements. The pregnancy should be followed up to determine outcome, including spontaneous or voluntary termination, details of the birth, and the presence or absence of any birth defects, congenital abnormalities, or maternal or newborn complications.

Pregnancy should be recorded on the Pregnancy Report Form. Pregnancy follow-up should be recorded on the same form and should include an assessment of the possible relationship to the study drug of any pregnancy outcome. Any SAE experienced during pregnancy must be reported as appropriate.

If any male subject's partner becomes or is found to be pregnant during the male subject's treatment with the investigational product, the Investigator must record and submit this information on a Pregnancy Report Form as described above.

11.4.3. Other Safety Considerations

Any significant changes noted during interim/final examinations, procedures or any other potential safety assessment should also be recorded on the appropriate AE or SAE eCRF.

For additional information, Investigators should contact:

PPD Medical Support Center

[contact]Telefax:[name]

11.5. Expedited Safety Reporting

Adverse drug reactions (ADRs) that are suspected, serious, and unexpected are subject to expedited reporting. Reports which add significant information on specificity or severity of a known, already documented serious ADR constitute unexpected events. For example, an event more specific or more severe than described in the protocol under safety assessments would be considered "unexpected". Specific examples would be (a) acute renal failure as a labeled ADR with a subsequent new report of interstitial nephritis and (b) hepatitis with a first report of fulminant hepatitis.

The purpose of expedited reporting is to make regulators, investigators, and other appropriate people aware of new, important information about serious adverse product reactions. Therefore, such reporting will generally involve events previously unobserved or undocumented. Accordingly, expedited reporting will ordinarily be inappropriate for adverse drug reactions that are serious but expected.

In accordance with local regulations, pSivida will notify investigators of all SAEs that are suspected (probably or possibly related to the investigational product) and unexpected (i.e., not previously described in the Investigator's Brochure).

Investigators will be notified about these events through the use of an expedited safety report (ExSR).

Other important findings which may be reported by the sponsor as an ExSR include: increased frequency of a clinically significant expected SAE, an SAE considered associated with study procedures that could modify the conduct of the study, lack of efficacy that poses significant hazard to study subjects, clinically significant safety finding from a nonclinical (e.g., animal) study, important safety recommendations from a study data monitoring committee, or sponsor decision to end or temporarily halt a clinical study for safety reasons.

Upon receiving an ExSR from pSivida, the Investigator must review and retain the ExSR with the Investigator's Brochure. Where required by local regulations or when there is a central IRB/EC for the study, the sponsor will submit the ExSR to the appropriate IRB/EC. The Investigator and IRB/EC will determine if the informed consent requires revision. The Investigator should also comply with the IRB/EC procedures for reporting any other safety information.

